## **Section 5.0 Research Design**

- 5.1 Liver marker implantation: Under CT or ultrasound guidance, a marker will be implanted into the liver tumor in a fashion similar to liver tumor biopsy and a stent placement. Prophylactic antibiotics will be given to prevent infection. The marker position and geometry will be documented on the simulation CT scan for planning SRT.
- 5.2 SRT:
  - 5.2.1 Machine: Novalis with 6 MV photons will be used for imaging guided SRT.
  - 5.2.2 Doses: Doses of 40, 50, 60 or 70 Gy (daily doses of 8, 10, 12 or 14 Gy in 2 weeks) will be prescribed to 90% isodose line. The prescription isodose volume should encompass the entire PTV. The subjects will be divided into groups of 5

to receive escalating doses of the SRT. The first group will receive a daily dose of 10Gy (Dose Level II). The next group will be enrolled only after the first group has been observed for 4 weeks following the SRT to document any side effects. The observation period will be used for every increase in dose level. Each subject will only receive one dose level of the SRT.

5.2.3 Localization, Immobilization and Simulation: A body-fix bag will be used for treatment simulation and delivery. Infrared markers will be attached to the patient's chest and abdomen in suitable positions to yield a good breathing signal. A 4D CT scan of abdomen will be performed for treatment planning. Treatment Planning: Following transfer to the treatment planning system, the CT scan may be correlated by imaging fusion with a MRI scan for contouring tumor volume. Integrated tumor volume (ITV) will be generated. The planning target volume (PTV) is defined as ITV plus individualized margins, which will be determined by a 4D CT scan. The uniformity requirement will be +10% -5% of the total dose at the prescription point within the tumor volume. The IMRT may be used if there is a benefit of decreasing tissue complications. The dose to the kidney will require careful monitoring and kidney volumes must be defined on simulation fields. The percent of total kidney volume (defined as the sum of the left and right kidney volume) receiving 15 Gy (3 Gy per fraction) should be required to be less than 35% of the total kidney volume. The maximum dose to any point within the spinal cord should not exceed 15 Gy (3 Gy per fraction). At least 700 ml or 35% of normal liver (entire liver minus cumulative GTV) should receive at total dose less than 15 Gy (3 Gy per fraction). The maximum point dose to the stomach or small bowel except duodenum should not exceed 80% of prescription dose. An isodose distribution of the treatment at the central axis indicating the position of kidneys, liver and spinal cord is required. The treatment plans should be optimized using dose volume histograms of any irradiated vital organ.

5.2.4 Treatment Delivery: The planning data containing the coordinates of tumor isocenter, the external infrared markers, and the implanted marker are transferred to the ExacTrac Adaptive Gating platform. The daily initial positioning will be performed using lasers and skin marks. The target isocenter will be verified on daily x-rays. If the patient meets the criteria of breath gating, treatment delivery is accomplished using the ExacTrac Adaptive Gating in combination with Novalis. External infrared markers attached to the patient's skin are used to determine the breathing pattern. The respiratory moving target is positioned, under infrared and x-ray guidance to a defined point within the patients' end expiratory breathing cycle. The gating reference level will be defined to evaluate target motion due to respiration. The size of beam-on window will be determined based on the target motion as detected by the 4D CT scan.

5.3 The study follow-up will coincide with the standard of care follow-up visits which will be 1 and 3 months after the completion of SRT. None of the tests or procedures is

performed more frequently than would be considered clinically standard. No procedures would be done exclusively for research purposes.

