Early studies from the international arena demonstrated that a high probability of local tumor control and a low likelihood of late normal tissue toxicity can be accomplished using focused radiotherapy techniques. More recently, Schefter et al have presented results from a phase I study of stereotactic body radiotherapy for the treatment of liver metastases. The dose was escalated from 36 to 60 Gy delivered in three fractions, with three patients in each dose regimen. Dose-volume constraints were specified such that a minimum of 700 ml of unaffected liver could receive no more than 15 Gy (over three fractions). Additional dosimetric constraints were placed on the total kidney volume (no more than 5 Gy per fraction to no less than 35% of the total volume), and on the spinal cord, stomach, and small intestine (maximum doses of 18 Gy, 30 Gy and 30 Gy respectively). No dose-limiting toxicity was observed at any dose level.

Following the methodology of Schefter et al, one can apply the linear-quadratic formalism for radiation cell killing to “equate” schemes that vary the dose/fraction and number of fractions. This concept of biologically equivalent dose (BED) says that the total effect is given by:

$$(nd) \left\{ 1 + d \frac{\alpha}{\beta} \right\}$$

where n is the # of fractions and d is the dose/fraction. The “alpha-beta ratio” characterizes the radiation response of a particular tissue; a higher value is indicative of a tissue that responds acutely to the effects of radiation. Due to their highly proliferative nature, most tumors fall into this category. Because prolonging the treatment time introduces a sparing (repair) effect in acutely responding tissues, there is significant motivation to deliver radiation in larger fractions over a shorter time.

While the dose-fractionation scheme employed by Schefter et al resulted in no significant morbidity, we propose a slightly more conservative dose escalation study as follows:

Dose Level	# Patients	# Fractions	Dose/fraction	Total Dose	Equivalent dose in 2 Gy/fractions
I	3-6	5	8 Gy	40 Gy	60.0 Gy
II*	3-6	5	10 Gy	50 Gy	83.3 Gy
III	3-6	5	12 Gy	60 Gy	110.0 Gy
IV	3-6	5	14 Gy	70 Gy	140.0 Gy

\*Starting dose level is Dose Level II.

For comparison, the 3 x 12 Gy arm in the Schefter study is equivalent to a total dose of 66 Gy in 2 Gy fractions, while the 3 x 20 Gy arm is equivalent to 150 Gy. All calculations assume an alpha/beta ratio of 10.

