Likewise, this study will follow the dose-volume constraints used by Schefter et al . Using the Novalis to deliver radiation, and excluding patients with a maximum tumor diameter of  $\geq 8$  cm, these criteria are easily achievable.

Data  have shown that radiological response rates to modern partial external radiotherapy of HCC are of the order of 50-70%. Single center studies show a strong dose-response relationship when doses  $>50$  Gray are given .

An autopsy series of patients who received 50-70 Gray showed evidence of tumor regression, but not eradication of HCC  It suggests that higher dose is required to eradicate HCC.

Recently, a study (the abstract is published in the July volume of the 2007 ASCO annual meeting) evaluated the effect of Cyberknife stereotactic radiosurgery (SRS) for both small primary non-resectable HCC (23 lesions in 22 patients), and advanced HCC with portal vein tumor thrombosis (PVTT) (9 lesions in 9 patients). The total SRS doses treated were 30-39 Gy (median, 36 Gy) to the 70-85%, 3 fractions and the target volume was of 3.6-57.3 cc (median, 25.2 cc). After median follow up of 10.5 months, a complete response (CR) was achieved in 10 lesions, a partial response (PR) in 13 lesions (CR+PR was 71.9%), stable disease in 6 lesions, and disease progression in 3 lesions. The level of serum alpha-fetoprotein after the treatment was decreased significantly in 17 patients (54.8%)  
Complications greater than grade 3 were observed in two patients. These results suggest that Cyberknife SRS could be considered as an effective and safe treatment for primary HCC. For PVTT, Cyberknife SRS as the only curative tool, and produced acceptable local control in this study.

The issue of respiratory motion has long been recognized as a major limitation in the management of radiotherapy patients. The limitations are manifest both in conventional

imaging for target localization, and in the delivery of radiotherapy itself. Respiratory motion during computed tomography (CT) scanning causes artifacts that distort the size, shape, and density of objects within the image, and introduce uncertainty in their location. Larger radiation fields are therefore required to ensure adequate coverage of the target anatomy. As a consequence, greater volumes of normal tissue are irradiated, which subsequently limits the therapeutic dose that can be delivered.

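### Section 2.0 says a cited phase I study's dose-volume limits will be followed, but Section 5.2.3 sets a different bowel cap, gives the duodenum no limit and adds an undefined liver alternative

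*Combined protocol and SAP*

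**What the plan says.** Section 2.0 (Introduction, under CRT and IMRT) summarises a phase I study of stereotactic body radiotherapy for liver metastases, given in three fractions. The limits it reports are:

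- liver: "a minimum of 700 ml of unaffected liver could receive no more than 15 Gy";
- kidney: "no more than 5 Gy per fraction to no less than 35% of the total volume";
- spinal cord, "stomach, and small intestine (maximum doses of 18 Gy, 30 Gy and 30 Gy respectively").

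It then commits this trial without qualification: "this study will follow the dose-volume constraints used by" that study. It also leans on that study's safety record. The cited scheme, it says, "resulted in no significant morbidity, we propose a slightly more conservative dose escalation study".

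Section 5.2.3, which holds the treatment-planning rules, reads differently. For bowel: "The maximum point dose to the stomach or small bowel except duodenum should not exceed 80% of prescription dose". For liver: "At least 700 ml or 35% of normal liver (entire liver minus cumulative GTV) should receive at total dose less than 15 Gy", at 3 Gy per fraction. The cord maximum is 15 Gy (3 Gy per fraction), and less than 35% of total kidney volume may receive 15 Gy (3 Gy per fraction).

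Neither section mentions or explains the differences.

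**The concern.** A reader of Section 2.0 would conclude that stomach and small bowel are held to a fixed 30 Gy maximum. Under Section 5.2.3 the limit rises with the dose level being tested, so prescribed dose and permitted bowel dose escalate together. The duodenum is taken out of the rule and given no number. The liver rule offers two criteria without saying whether either is enough or which governs.

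This touches the trial's main question. Small-bowel toxicity is named in the primary objective (1.1.1.1), and grade 4 or 5 gastrointestinal toxicity is a DLT (10.1). Section 5.4.2 lists small bowel obstruction among long-term effects, whereas the DLT window is 30 days from the start of treatment. The escalation rules may therefore miss late bowel injury, which gives the planning limits more weight.

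The cited study's lack of morbidity is used to introduce these dose levels. As summarised, that result was obtained under a fixed bowel maximum, so it lends less support to escalation under a looser one.

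**Working it through.** **Inputs.** Prescriptions are 40, 50, 60 and 70 Gy in 5 fractions at Levels I to IV, starting at Level II (Sections 2.0, 5.2.2, 10.1). The cited bowel limit is 30 Gy in 3 fractions (2.0). This trial's bowel cap is 80% of prescription (5.2.3). On alpha/beta, Section 2.0 states: "All calculations assume an alpha/beta ratio of 10". No bowel-specific value is given, so 3 is used as an assumed alternative.

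**Formula.** EQD2 = D × (d + a) / (2 + a), where D is total dose, d is dose per fraction and a is alpha/beta.

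**Reproducing the protocol's figures (a = 10).**

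- 5 × 8 Gy: 40 × 18/12 = 60.0
- 5 × 10 Gy: 50 × 20/12 = 83.3
- 5 × 12 Gy: 60 × 22/12 = 110.0
- 5 × 14 Gy: 70 × 24/12 = 140.0
- 3 × 12 Gy: 36 × 22/12 = 66
- 3 × 20 Gy: 60 × 30/12 = 150

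All six agree with Section 2.0.

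**Bowel.** The cited limit is 30 × 20/12 = 50.0 Gy at a = 10, and 30 × 13/5 = 78.0 Gy at a = 3.

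| Level | Cap (Gy in 5 fractions) | Gy per fraction | EQD2, a = 10 | Ratio to 50.0 | EQD2, a = 3 | Ratio to 78.0 |
|---|---|---|---|---|---|---|
| I | 32 | 6.4 | 43.7 | 0.87 | 60.2 | 0.77 |
| II (start) | 40 | 8.0 | 60.0 | 1.20 | 88.0 | 1.13 |
| III | 48 | 9.6 | 78.4 | 1.57 | 121.0 | 1.55 |
| IV | 56 | 11.2 | 98.9 | 1.98 | 159.0 | 2.04 |

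The direction does not hinge on alpha/beta. At Level II, 40(8 + a) − 30(10 + a) = 20 + 10a, which is positive for every positive a. At Level I, 32(6.4 + a) − 30(10 + a) = 2a − 95.2, which is negative for any a below 47.6.

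**Duodenum.** No section gives a numerical limit. The only other relevant text is the general instruction in 5.2.3 to optimise plans with dose-volume histograms, which supplies no number.

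**Liver volume.** The two criteria are equal at 700 / 0.35 = 2,000 ml of normal liver.

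- If either suffices, the floor is below 700 ml for any smaller liver. For assumed volumes of 1,200, 1,500 and 1,800 ml it is 420, 525 and 630 ml. At 2,000 ml or more it stays at 700 ml.
- If both are required, the floor is never below 700 ml.

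**Limits that are stricter in 5.2.3.**

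- Liver dose part, 15 Gy in 5 versus 3 fractions: 16.25 versus 18.75 Gy at a = 10 (ratio 0.87); 18.0 versus 24.0 at a = 3 (0.75).
- Cord, 15 Gy in 5 versus 18 Gy in 3: 16.25 versus 24.0 Gy at a = 10 (0.68); 18.0 versus 32.4 at a = 3 (0.56).
- Kidney: the total is the same (5 × 3 = 3 × 5 = 15 Gy) at a lower dose per fraction. The volume condition also differs. As printed, the cited rule keeps at least 35% of kidney volume at or below the dose, while 5.2.3 lets less than 35% reach it.

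**The case against.** Section 2.0 is background and Section 5.2.3 is the operative planning section. For stomach and non-duodenal small bowel, the 80% rule can be applied at every level, and most planners would follow it. On that view the fault is one inaccurate introductory sentence. Three-fraction limits also cannot move unchanged into a five-fraction schedule, so some numerical change was to be expected. An alpha/beta of 10 was chosen for comparing regimens, not for bowel tolerance. The liver point depends on how one word is read, and the duodenal departure rests on the silence of a short summary of a study not available here.

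Much of this is fair as qualification. The liver point is an ambiguity, not a demonstrated loosening. What is certain about the duodenum is only that this protocol gives it no number. Adaptation to five fractions could account for the kidney rule and for the liver dose part, which keep the same 15 Gy total.

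It does not account for the bowel rule. The conversion already allows for fractionation, and from Level II the cap exceeds the cited limit at any positive alpha/beta. Nor does it explain the duodenal exception or the 35% alternative. Calling Section 2.0 background does not rescue an unqualified statement that the cited limits will be followed, on which a reader judging safety would rely.

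**Conclusion.** The concern holds. The two sections contradict each other on a safety limit for an organ in the primary objective and the DLT definition, and the conflict applies from the starting dose. After conversion, the permitted bowel maximum is about 13% to 20% above the cited limit at Level II, about 55% to 57% above it at Level III and about twice it at Level IV. At Level I it is 13% to 23% below. These ranges span alpha/beta 10 (the protocol's value) and 3 (assumed).

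They compare permitted maxima, not expected exposures, and they rest on the protocol's own summary of the cited study. The support drawn from that study is weakened for stomach, small bowel and duodenum, and possibly for liver volume. It is not weakened for cord or kidney, and it is one of several supports that Section 2.0 cites. The conflict should be resolved, not left to the planner.

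**What to change.** Reconcile Section 2.0 with Section 5.2.3 so that the statement about following the cited study's limits and the planning limits agree. The amendment should cover the stomach and small-bowel rule, the duodenal exception and how the duodenum is handled, and whether the 700 ml and 35% liver criteria are alternatives or joint requirements. Any departure from the cited limits that is kept should be named and explained, including those in the stricter direction. The claim of a more conservative scheme should be reread in that light.

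Which limits are right is for the sponsor's clinical and physics staff. The converted doses above serve only for comparison and are not candidate limits. The cost is a wording amendment to the Introduction, Section 5.2.3 or both, with clinical and physics sign-off. Sample size and visits do not change.

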#### 5.4 Toxicity:

- 5.4.1 Implantation of a liver marker: The side effects of implantation will be similar to the needle biopsy of liver tumor and the stent placement including but not limited to tumor seeding, foreign body, infection, bleeding, pain at local area, and dislocation of the marker.
- 5.4.2 SRT: Short term side effects include but not limited to skin reaction, local hair loss, fatigue, abdominal pain, nausea, vomiting, diarrhea, increasing liver function abnormality, GI bleeding or perforation which may require surgical intervention. Long term side effects are less likely to occur but if they do occur are more likely to be permanent. They include local hair loss, liver function abnormality, diarrhea, small bowel obstruction which may require surgical intervention, spinal cord injury which could result in paralysis, kidney function abnormality.

#### 5.5 Dose Modifications:

Radiation therapy will be held if the AGC is  $< 500/\mu\text{L}$  and/or the platelets are  $< 50,000/\mu\text{L}$ . Upon recovery of the AGC to  $\geq 500/\mu\text{L}$  and platelets to  $> 50,000/\mu\text{L}$ , radiation therapy will resume at the full planned daily dose.

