## Section 7.0 Study Parameters

### 7.1 Laboratory/imaging Studies:

Parameter	Baseline	Pre- and post-SRT therapy	Post-Treatment Follow-up
History	X	X b	a
Physical examination	X	X b	a
Weight	X	X	a
Vital signs	X	X	a
Performance status (Karnofsky)	X	X	a
CBC, differential, platelet count	X	X Post- SRT	a
Comprehensive metabolic panel (including bilirubin, alk phos, AST, ALT, )	X	X Post- SRT	a

Fill out pain assessment card	X	X Post-SRT	a
AFP	X	X post-SRT	a
PT, PTT, INR	X	X Post-SRT	a
CT	X	X simulation	
MRI	X	X Post-SRT	a
Serum pregnancy test	prn		

*a - will be done at one month and 3 months after the completion of SRT*

*b – A brief physical exam and history will be performed*

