#### Endpoints

Toxicity will be graded by NCI Common Toxicity Criteria (CTC Version 3.0). Due to delayed toxicities attributable to radiotherapy, all toxicities observed within 1 month after SRT will be scored. DLT is defined as any of following toxicities, that is possibly, probably or definitely related to SRT occurring within 30 days from the start of treatment:

- a) grade 4 or 5 hepatic
- b) grade 4 or 5 gastrointestinal
- c) grade 4 or 5 thrombocytopenia
- d) grade 4 hepatic liver enzyme elevations persisting for  $\geq 5$  days
- e) any adverse event requiring interruption of therapy by  $\geq 2$  weeks (14 calendar days). This does not include patient desire to discontinue therapy. It does include failure for thrombocytopenia to improve to a level of 80 requiring interruption of therapy.
- f) Any grade 5 treatment-related adverse event

The MTD of SRT is defined as the highest dose level at which no greater than 2 DLT is observed in 6 patients.

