## Appendix II

### Schedule of Activity

	Screening/Baseline	Liver Marker Implant Procedure	1-7 Days Post Implant	SRT planning,	Start SRT	End SRT	1 month Post SRT	3 Months Post SRT
History & Physical	x		x	x	x	x	x	x
CT abdomen/pelvis	x	x		x				
MRI abdomen/pelvis	x			x				x
biopsy	x							
Inclusion/Exclusion	x							
Informed consent	x							
CT or U/S guided marker implant		x						
AFP	x			x			x	x
CBC with diff	x		x	x			x	x
INR	x							
complete chemistry pannel	x		x	x			x	x
Chest X-ray or Chest CT	x							
Record adverse events		x	x	x	x	x	x	x

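### No CBC or chemistry panel is scheduled between the first and last SRT fraction, and at most one scheduled draw falls inside the 30-day DLT window

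*Combined protocol and SAP*

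**What the plan says.** **Hold rule.** Section 5.5 (Dose Modifications) says "Radiation therapy will be held if the AGC is" below 500/µL and/or platelets are below 50,000/µL. Treatment resumes at the full daily dose on recovery. No testing times are given.

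**Laboratory DLTs.** Section 10.1 (Endpoints) lists (c) "grade 4 or 5 thrombocytopenia" and (d) "grade 4 hepatic liver enzyme elevations persisting for" 5 days or more. Item (e), interruption of 2 weeks or more, includes platelets that fail to recover to 80.

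**DLT window and definition.** The same subsection limits DLTs to events "occurring within 30 days from the start of treatment", but just before that it says "all toxicities observed within 1 month after SRT will be scored". Section 9.3 makes any toxicity of grade 4 or above a DLT, with no persistence condition.

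**Schedules.** In the Section 7.1 table, the row "CBC, differential, platelet count" and the metabolic panel row are marked at baseline, once post-SRT without a date, and at follow-up, which "will be done at one month and 3 months after the completion of SRT". In Appendix II, the CBC row and the "complete chemistry pannel" row are marked at screening, 1 to 7 days after implant, SRT planning, and 1 and 3 months post SRT. Start SRT and End SRT are blank for both tests, although history and physical and adverse events are marked at both visits.

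**The concern.** The hold rule can act only on a count that someone has taken, and the laboratory DLTs can be scored only from results that exist. If the tests are not scheduled, detection in a patient without symptoms depends on a clinician's choice to order them.

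Safety is the primary objective, and Section 5.4.2 names worsening liver function among the short-term effects of SRT. Escalation turns on whether 0, 1 or 2 of 3 patients have a DLT, so a single unseen event can change the decision. Any such error runs in one direction, toward a higher dose.

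**Working it through.** **1. Scheduled CBC or chemistry draws, counted from the two tables**

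| Period | Section 7.1 | Appendix II |
|---|---|---|
| Between first and last fraction | 0 | 0 |
| After SRT, before the 1-month visit | at most 1, undated | 0 |
| At 1 month after SRT | 1 | 1 |

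**2. When the 1-month draw falls**

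Inputs: five fractions (Section 2.0 dose table, Section 10.1) within 2 weeks (Abstract). Assumptions: day 1 is the first fraction; the course ends between day 5 (consecutive days) and day 14; a month is 28 to 30 days.

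- Earliest: 5 + 28 = day 33.
- Latest: 14 + 30 = day 44.
- If the 30-day window closes on day 30, the draw is 33 − 30 = 3 to 44 − 30 = 14 days too late.
- If the window is taken to close on day 31, the draw is 2 to 13 days too late. It is outside under either convention.

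**3. Draws from the start of SRT to the end of each DLT window**

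| Window in Section 10.1 | Section 7.1 | Appendix II |
|---|---|---|
| 30 days from first fraction | at most 1 | 0 |
| 1 month after SRT | at most 2 | 1, at the boundary |

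If the undated Section 7.1 draw is taken on the last treatment day (day 5 to 14), then 30 − 14 = 16 to 30 − 5 = 25 days of the 30-day window follow with no further scheduled test.

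**4. What the laboratory DLTs need**

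- (c) needs a count taken while platelets are low.
- (d) needs at least two panels 5 or more days apart. The 30-day window holds at most one. Under Section 9.3 a single grade 4 panel would be enough, so the same result can be a DLT in one section and not in the other.
- (e), in its platelet part, needs a count to start the interruption and later counts to show failure to recover.

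**5. Room before a hold**

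Section 3.1.7 admits patients with platelets of 60 × 10⁹/L, which is 60,000/µL. A fall of more than 60,000 − 50,000 = 10,000/µL, or 10,000/60,000 = 16.7%, reaches the hold level. This measures the distance to a hold, not to a DLT.

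**6. Link to the stated operating characteristics**

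Section 10.3 gives 68% for not escalating at a true DLT rate of 35% and 66% for escalating at 20%, with 6 patients. Both reproduce if escalation requires at most 1 DLT in 6:

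- 1 − 0.65⁶ − 6(0.35)(0.65⁵) = 1 − 0.0754 − 0.2437 = 0.681.
- 0.80⁶ + 6(0.20)(0.80⁵) = 0.2621 + 0.3932 = 0.655.

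Both count every DLT as seen. If only a share s of DLTs is detected, the rate p becomes p × s and the chance of not escalating falls. The documents give no value for s, so the direction is known but the size is not.

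**The case against.** The strongest reply is that the protocol has other safeguards and leaves on-treatment tests to standard care. Section 9.3 provides weekly review of patients during SRT, real-time faxing of outside laboratory results, and power to halt escalation on any hazard signal. Section 5.5.3 requires a CBC for fever. Section 5.3 says tests will not exceed the clinical standard. These points are fair, and clinicians may well draw blood during SRT. But weekly review names no blood test, faxing governs how results travel rather than when tests are taken, and the CBC needs a fever. None of them requires a count during treatment.

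Repeat testing is also partly implied. Section 5.5 resumes SRT only on recovery, which cannot be known without a new count, so no separate rule for counts during a hold is needed. Section 9.3 asks for onset and resolution dates of every adverse event, which implies some retesting after a known grade 4 enzyme result. What it does not give is an interval that would settle 5-day persistence.

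The course is only five fractions, the side-effect list in Section 5.4.2 (which is not exhaustive) names no cytopenia, and the documents give no expected platelet fall. On-treatment holds may therefore be rare. The two DLT windows and the differing DLT definitions would be inconsistencies under any schedule. They matter here because they decide which draws count.

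A reader might also infer, from the four-week wait in Sections 5.2.2 and 9.3, that escalation could go ahead before the last patient's 1-month draw. The documents do not support this. The Dose-escalation Rules in Section 10.1 require at least 1 month of observation in all 3 patients first. The reference there to surgery is evidently a slip for SRT, since Section 10.2 waives one month of observation after SRT only for the expansion phase. What remains is that no sentence says the laboratory result must be reviewed before the decision.

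**Conclusion.** The point holds. No CBC or chemistry panel is scheduled between the first and last fraction in either table, and this count needs no assumption. Within 30 days of the first fraction the scheduled draws number 0 (Appendix II) or at most 1 (Section 7.1). That the 1-month draw falls outside the window rests on a course ending on day 5 to 14 and a month of 28 to 30 days. Laboratory DLTs (c), (d) and the platelet part of (e) therefore cannot be reliably detected on schedule, and a missed one would tend toward escalation.

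Two further inferences should be resisted. One is that the Section 10.3 probabilities are wrong by a known amount: they reproduce, and no detection rate is given. The other is that interruption DLTs are untouched because they are clinically evident: item (e) has a platelet component. The change should be made, but the documents do not show that any event would in fact be missed.

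**What to change.** 1. Make Section 7.1 and Appendix II agree. Schedule CBC with platelets and chemistry at one on-treatment time before the last fraction, and again at the existing End SRT visit. Tie the first draw to a fraction rather than to the weekly visit, because with five consecutive daily fractions the weekly visit may coincide with End SRT. The clinical team should choose the day.
2. State one DLT window in Section 10.1, running through 1 month after completion of SRT, to match the one-month observation before escalation. Correct surgery to SRT in that rule. Require the 1-month draw to fall inside the window and to be reviewed for every cohort patient before escalation.
3. Use one DLT definition in Sections 9.3 and 10.1. If the 5-day persistence condition is kept, require a repeat panel at least 5 days after a grade 4 enzyme result.

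The cost is a schedule amendment and one or two routine blood draws per patient: one beyond Section 7.1, whose undated draw would become the End SRT draw, or two beyond Appendix II. A repeat panel is added only after a grade 4 enzyme result. The Section 5.3 statement on standard test frequency should be checked against the new schedule.
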